#### 10.5.1. Safety

This is the first administration of RTS,S/AS02D to infants and therefore the sample size of this Phase 1/2 safety study is limited to 200. Therefore only large differences in the frequencies of SAEs can be detected with reasonable power. The data set will be examined, comparing the rates of SAEs at the Medical Dictionary for Regulatory Activities (MedDRA) preferred term level. A sample size of 200 has the power to detect differences in the rates of safety endpoints (SAEs at the MedDRA preferred term level) as shown in Table 26. All calculations were performed with PASS 2000, using an asymptotic test for difference in proportions, type I error rate of 5% and no correction for multiplicity.

# Table 26Differences in safety endpoints (SAEs at the MedDRA preferred term
level) between treatment groups that can be detected with 80%
power for varying baseline rates

Frequency of events for Engerix-B	Frequency of events for RTS,S/AS02D	Power to detect difference (number per group equals 100)
1%	12%	80%
3%	15%	80%
5%	19%	80%
10%	26%	80%

# 10.5.2. Sample size for secondary endpoint immunology of Hepatitis B response

This study will compare the immunogenicity of RTS,S/AS02D to Engerix-B. A noninferiority approach will be used to calculate the power of the study for the comparison of seroprotection rates and geometric mean titers of anti-HBs antibodies. The assessment of the anti-HBs antibody immune response will be based on approximately 200 evaluable subjects (100 subjects per group). This sample size will have 90% power at a 2.5% significance level using a one-sided equivalence test of proportions when the proportion that are seroprotected in the control group (subjects vaccinated with Engerix-B) is at least 0.97 and the proportion in the RTS,S/AS02D group is 0.97 and the maximum allowable difference between these proportions that still results in equivalence (the range of equivalence) is 0.10 (PASS 2000, one sided equivalence test of proportions, alpha = 2.5%).

Similarly this sample size will provide 98.5% power to demonstrate at a 5% significance level using an equivalence of means test, that the lower limit of a two sided 95% confidence interval on the GMT ratio of anti-HBs antibodies (RTS,S/AS02D vaccine

group over Engerix-B vaccine group ) is greater than 0.5 (2 fold decrease). (PASS 2000, equivalence of means, alpha = 5%). The standard deviation used for this calculation was 0.52 (computed on log base 10 transformed titers) and was derived from a GSK Biologicals study (Malaria-034) on 67 subjects which received three doses of RTS,S/AS02D administered at a 0, 1, 2 months schedule.

# 10.5.3. Sample size for secondary endpoint proof of concept

Assuming an attack rate of 75% in the Control Group over the 3-month surveillance period (Personal Communication [name] September 2004: data from a study performed in Ilha Josina in 2001, July to September in children 7 to 18 months), 100 evaluable subjects per group are needed in order to have 90% power to show a Vaccine Efficacy (=1-hazard ratio) of 45% (Pass 2000, Log rank Survival, alpha=0.05, based on the assumption that the hazard rates are proportional). This is equivalent to an attack rate in the Vaccinated Group of 53.3%. Using proportion of subjects with malaria infection over the surveillance period, a Vaccine Efficacy (=1-risk ratio) of 29% can be detected with 90% power.

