# 1.4. Rationale for the study design

There are two reasons why the RTS,S/AS02D candidate malaria and hepatitis B vaccine is being developed for delivery through the infant Expanded Program on Immunization (EPI) of the World Health Organization (WHO). Firstly, the vaccine is being developed to prevent severe malaria disease which occurs from about 4 months of age coinciding with the time that maternally-acquired immunity wanes [Snow 1990, Snow 1994]. Secondly the EPI has been highly successful at increasing the coverage of basic vaccines across the developing world. With the goal of integration into the EPI infant regimen, a 0, 1, 2 month schedule has been evaluated in children and the final dose volume has been adjusted to 0.5 mL to be compatible with the standard syringes used by EPI (see Section 1.3.2).

Although RTS,S/AS02D is primarily being developed as a vaccine against malaria, the particles of RTS,S contain HBsAg and the vaccine induces high seroprotection rates against hepatitis B (see Section 1.2.2). Therefore it is logical to propose that, in malaria endemic regions, RTS,S/AS02D replaces the existing hepatitis B vaccine in the infant regimen. This approach has the advantage that adding malaria immunization to the EPI schedule requires no extra vaccination clinic visits in the first year of life, which is more practical for parents and EPI services.

As the next step in the development path, this study examines the feasibility of giving RTS,S/AS02D to infants in the EPI age range; three doses of RTS,S/AS02D will be given at 10, 14 and 18 weeks of age, staggered with the administration of DTPw/Hib at 8, 12 and 16 weeks of age. The control arm will receive Hepatitis B vaccine at the times RTS,S/AS02D is given. As this is the initial assessment of vaccine safety in infants, the conduct of this study will precede studies of the coadministration of RTS,S/AS02D with

EPI vaccines. In this study, the licensed vaccines used are Engerix-B® (GlaxoSmithKline Biologicals) and TETRActHibTM (Aventis Pasteur).

Because this is an experimental regimen of hepatitis B immunization, infants at high risk of hepatitis B infection will be excluded from the trial. Infants born to women who are chronic carriers of hepatitis B virus (HBV) will receive the licensed vaccine in a regimen starting at birth (refer to Section 5.1.10.2.1).

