#### 5.1.11. Vaccination process

The vaccines RTS,S/AS02D and Engerix-B will be packaged in identical boxes and will be identified by a treatment number. The unique treatment number will identify all doses of these vaccines administered to each subject. After randomization the treatment number assigns the subject to one group or another in a blinded way. The administration of the vaccine TETRActHib is not blinded; however it will be identified by a treatment number.

The treatment number will be issued sequentially at Clinic Visit 2. Each subject will retain the same treatment number for their subsequent vaccine doses. The treatment number will be recorded on the subject's Clinic Form after the vaccine has been administered; information from the Clinic Form is subsequently transferred to the Case Report Form. The Clinic Form and Case Report Form link the subject number and the treatment number.

• All vaccines will be administered by the intramuscular route to the antero-lateral thigh: left thigh RTS,S/AS02D or Engerix-B and right thigh TETRActHib. Subjects who receive their vaccination with in the incorrect leg will continue to receive subsequent blinded vaccinations of RTS,S/AS02D or Engerix-B and unblinded vaccinations with TETRActHib as normal. The fact that the vaccine was administered in the wrong limb will be documented and they will be eliminated from the According to Protocol Cohort for Safety.

Vaccinations will take place at the EPI clinic of Ilha Josina Health Center *and Taninga Health Center (Amended 29 June 2005)*. All vaccinations will be given by a qualified person; a nurse or a doctor or a 'medical agent of preventative medicine'. A staff member experienced in the resuscitation of children will be available at all vaccination sessions. Facilities and equipment will be available to give emergency treatment in the case of an anaphylactic reaction following administration of vaccines. All children will be observed for an hour after the administration of vaccine to evaluate and treat any acute adverse events.

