#### 10.9.3.2. Vaccine efficacy

Time to first infection of *P. falciparum* will be examined using Kaplan-Meier curves for both groups. The distribution will be compared with the Wilcoxon test (if efficacy varies with time) or the Log-rank test (if it does not). Vaccine Efficacy will be assessed using Cox regression models. Vaccine efficacy is defined as 1-R where R is the hazard ratio of the RTS,S/AS02D group versus the Engerix-B group (with 95% CI). Crude and adjusted estimates for prognostic/stratifying factors (see Section 10.9.3.3) will be presented.

Cox regression assumes proportional hazards throughout the follow-up period. This assumption will be checked by plotting by group the log of the cumulative hazard against the log of time. Under the assumption of proportionality of the hazard, both curves should be parallel. A test based on the Schoenfield residuals will be performed.

If there is strong evidence that the hazard is not constant over the surveillance period, then alternative approaches to analyze the data will be examined according to the following:

• Cox regression models with time varying covariates, using fractional polynomials to identify the function of the time that best fits. The following functions of the time will

be explored: -2, -1,  $-\frac{1}{2}$ , log, identity,  $\frac{1}{2}$ , 2, 3. The Akaike's criterion and the Schwarz Bayesian criterion will be explored.

• Piecewise Cox regression model, partitioning the surveillance period in three periods based on the equal number of events

For the assessment of the parasite density at Month 6, a 2x2 table presenting the frequency of positive and negative will be presented. The effect of the group will be evaluated using the Fisher exact test. The geometric mean of those positive in each group will be calculated. Difference in geometric mean and 95% CI will be estimated. The effect of the group will be evaluated using the t-test. In case the assumptions of the t-test are not satisfied (normality of residuals and equal variance) a non-parametric Wilcoxon test will be used instead.

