## **Rationale/background for changes:**

In order to expedite the recruitment for this trial, a second health center will be used to recruit mothers and vaccinate infants in addition to the health center at Ilha Josina. This second health center, Taninga, is similar to that at Ilha Josina. All facilites available at Ilha Josina are also available at Taninga and all staff are trained to the same standard. It is proposed to carry out all procedures in exactly the same manner as for those mothers and infants recruited at Ilha Josina. A detailed description of the facilities available at the Taninga Health Center have been added to the protocol with this amendment

At the request of the Food and Drug Administration, a rationale for the proposed interim analysis at 1 month post final dose of vaccine has been added.

An error in the safety monitoring plan has been corrected. The text describing the laboratory values that would be made available to the DSMB was not logical. The text has been corrected in order to ensure the original intent of providing the maximum possible amount of laboratory data to the DSMB.

An error in the 'Process if the trial is suspended' has been corrected. It has been clarified that the DSMB may suspend the trial temporarily. However should it be necessary to stop the trial permanently, the responsibility lies with the Sponsor, GSK.

Details of the proposed CMI testing have been clarified

One of the GSK local study monitors ([name]) will not be taking part in the monitoring of this trial and has been removed from the document as a study contact.

One of the GSK authors was inadvertently left off the authorship list on the cover page. They have now been added. In addition, a number of new staff members at CISM/Hospital Clinic, Barcelona have been added to the list of authors

Amended text has been included in *bold italics* in the following section(s): Cover Pages:

- [name], Central Study Coordinator
- [name] Immunologist
- [name]
- [name], Immunologist

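### The 75% control attack rate is extrapolated to younger infants and a second catchment with little power margin, and Amendment 3 left the main efficacy test unstratified by health center

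*Protocol*

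**What the plan says.** Protocol section 10.5.3 begins "Assuming an attack rate of 75% in the Control Group over the 3-month surveillance period" and gives the source as a personal communication: "data from a study performed in Ilha Josina in 2001, July to September in children 7 to 18 months". On that basis "100 evaluable subjects per group are needed in order to have 90% power to show a Vaccine Efficacy (=1-hazard ratio) of 45" per cent, with the method given as "Pass 2000, Log rank Survival, alpha=0.05, based on the assumption that the hazard rates are proportional". The synopsis repeats the figures without the source.

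Infants enter at 6 to 12 weeks of age (section 4.3). Table 20 places active detection of infection at about 20 to 32 weeks of age.

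The rationale for Amendment 3 in Appendix H states that "a second health center will be used to recruit mothers and vaccinate infants in addition to the health center at Ilha Josina". Section 5.1.11, where "Vaccinations will take place at the EPI clinic of Ilha Josina Health Center" used to stand alone, now adds Taninga. Section 4.1.5.2 now calls Ilha Josina the closest center for most, no longer all, study children. The amendment's list of changed sections includes neither 10.5 nor 10.9.3.

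For the analysis, section 10.9.3.2 states: "The distribution will be compared with the Wilcoxon test (if efficacy varies with time) or the Log-rank test (if it does not"). Efficacy is then estimated by Cox regression, crude and adjusted. Section 10.9.3.3 puts the treatment-only estimate first and adjusts second, for age, barrio and distance from the health center.

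**The concern.** Power for time to first infection depends on the number of infections, and so on the control attack rate. The planning rate differs from the trial in two respects that could lower it:

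- **Age.** The source children were 7 to 18 months old. Trial infants are mostly younger while under surveillance, and section 1.4 speaks of "severe malaria disease which occurs from about 4 months of age coinciding with the time that maternally-acquired immunity wanes".
- **Catchment.** The rate comes from Ilha Josina alone. No transmission figure is given for Taninga. Section 1.3.3.3.1 reports higher transmission in Ilha Josina than in Manhiça in the earlier pediatric efficacy trial, so localities in this district can differ.

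One respect could raise it: the source months are July to September, and section 4.1.3 puts peak transmission at October to May.

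The second issue is the test. The protocol treats geographical area as prognostic, yet adding a second catchment did not change the main comparison, which pools both. If baseline hazards differ between centers, a pooled log-rank test loses power and the crude hazard ratio is pulled towards 1. This is the trial's efficacy read-out before larger infant studies (section 1.4.2), so power that can be kept at no cost is worth keeping.

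**Working it through.** **Inputs from the protocol.** Control attack rate pc = 0.75, hazard ratio 0.55 (1 − 0.45), 100 evaluable per group, alpha 0.05 (10.5.3); 1:1 allocation (6.4.1). Two-sided alpha is taken because it reproduces the stated figure; one-sided 0.05 would give 95.0%.

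**Reproducing the stated power**
- Vaccinated attack rate = 1 − (1 − pc)^0.55 = 1 − 0.25^0.55 = 53.35% (stated 53.3%).
- Expected events = 100 × (0.75 + 0.5335) = 128.3.
- Freedman power = Φ(√events × (1 − 0.55)/(1 + 0.55) − 1.96) = Φ(11.33 × 0.2903 − 1.96) = Φ(1.33) = 90.8%.
- Events needed for 90%: 125, that is 125 / (2 × 0.6417) = 97.4, so 98 per group against 100 planned.

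The stated 90% therefore reproduces. Schoenfeld's formula gives 92.3% and fits the protocol less well, so Freedman is used for power below.

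**Sensitivity to the control rate** (assumed range; same formula, 100 per group, HR 0.55)

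| Control rate | Events | Power | n per group for 90% |
|---|---|---|---|
| 85% | 149.8 | 94.4% | 84 |
| 80% | 138.7 | 92.8% | 91 |
| 75% | 128.3 | 90.8% | 98 |
| 70% | 118.4 | 88.5% | 106 |
| 65% | 108.9 | 85.8% | 115 |
| 60% | 99.6 | 82.6% | 126 |
| 50% | 81.7 | 74.7% | 154 |

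Power falls below 90% at a control rate of about 73% and below 80% at about 56%.

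**Age overlap.** Active detection runs from Day 90 to Day 180, about 13 to 26 weeks after first vaccination. An infant entering at 6 weeks is then about 19 to 32 weeks old, and one entering at 12 weeks about 25 to 38 weeks. Seven months is about 30 weeks, so the overlap with the source ages is partial.

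**Season.** With 30 births a month and 25% ineligible (10.5), about 22.5 infants a month can be enrolled: 220 / 22.5 is roughly 10 months. Surveillance will therefore include months inside the October to May peak.

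**Events lost through the second catchment.** Assume Ilha Josina stays at 75% and HR 0.55 holds in both centers. With a share w of infants from Taninga at control rate x, events = 100 × [(1 − w) × 1.2835 + w × (x + 1 − (1 − x)^0.55)]. Both w and x are assumptions.
- w = 25%: x = 60% gives 121.2 events, power 89.2%; 50% gives 116.7, 88.0%; 30% gives 108.2, 85.5%.
- w = 50%: x = 60% gives 114.0 events, power 87.3%; 50% gives 105.0, 84.5%; 30% gives 88.1, 77.8%.

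**Pooled against stratified log-rank.** Simulation with 4,000 trials per setting, 100 per group, exponential times grouped into two-week visits, half the infants per center, HR 0.55 and Ilha Josina at 75%:

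| Taninga rate (assumed) | Unstratified | Stratified by center | Gain |
|---|---|---|---|
| 60% | 87.5% | 88.6% | 1.1 points |
| 45% | 80.2% | 84.0% | 3.8 points |
| 30% | 70.5% | 78.9% | 8.4 points |

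When the two centers have the same rate, simulation shows no material loss from stratifying. A smaller Taninga share gives a smaller gain.

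**The case against.** The strongest reply is that nothing here is an error. Section 10.5.3 is expressly conditional on 75%, discloses the age, place and months of its source, and computes correctly. A reader might infer that the 90% is unsupported or that the trial is underpowered. The documents do not show that: they give no rate for infants of this age or for Taninga, and season points the other way. At 80% to 85% the power would be 93% to 94%.

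The age argument also has limits. Section 1.4 speaks of severe disease, whereas the endpoint is any parasitemia, and it places the waning of maternal immunity before surveillance starts. Nothing suggests lower transmission in Taninga, which section 4.1.2 places on the banks of the Incomati, and section 4.1.3 calls that river's flood plains ideal breeding ground. The wording of section 4.1.5.2 makes a half share for Taninga look high, so the simulated gains lean to the large side. All of this stands.

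On the test, a reader might infer that pooling the two centers invalidates the comparison. It does not: under 1:1 randomization the unstratified log-rank test is valid, and barrio and distance enter the adjusted estimate. But that adjustment comes second and does not reach the named test or the crude estimate, so the efficiency point survives.

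**Conclusion.** The point holds as one of thin margin and avoidable loss of efficiency. The 75% is an extrapolation across age and, since Amendment 3, across catchments. The 90% is correct at 75% but needs a control rate of about 73% or more, and the direction of any departure is not established. Leaving the main test unstratified costs nothing if the centers are alike and about 1 to 8 points of power if they differ as assumed above. Those gains rest on an assumed half share and assumed Taninga rates of 60% to 30%; the power figures rest on proportional hazards with HR 0.55 and 100 evaluable infants per group. Efficacy is a secondary objective, which limits the consequence.

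**What to change.** - **Main change.** In section 10.9.3.2, stratify the log-rank or Wilcoxon test and the main Cox model by health center (Ilha Josina, Taninga), and report attack rates by center and group. Keep the adjusted estimate of section 10.9.3.3 as the secondary one.
- **Secondary wording.** In section 10.5.3 and the synopsis, show power over control attack rates of about 50% to 85%, and say that 90% requires about 73% or more in the infants actually followed.

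The cost is wording and one stratification term from data already on record. The power statement becomes less favorable at the lower rates.

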# 10.6. Study cohorts to be evaluated

# 10.6.1. Total Vaccinated Cohort

The Total Vaccinated Cohort will include all vaccinated subjects for whom data are available. Thus, the total analysis of safety will include all subjects with at least one vaccine administration documented and the total analysis of immunogenicity/efficacy will include vaccinated subjects for whom data concerning immunogenicity/efficacy endpoint measures are available. The Total Vaccinated Cohort analysis will be performed per treatment actually administered.

# 10.6.2. According to protocol (ATP) cohort for analysis of safety

The ATP cohort for analysis of safety will include all evaluable subjects;

- who have received at least one dose of study vaccine according to their random assignment
- have sufficient data to perform an analysis of safety (at least one vaccine dose with safety follow-up)
- for whom administration site of study vaccine is known
- who have not received a vaccine not specified or forbidden in the protocol and for whom elimination criteria were not applied
- for whom the randomization code has not been broken except for when unblinding has been carried out by the DSMB for Safety Analysis.
- who meet all eligibility criteria.

# 10.6.3. According to protocol (ATP) cohort for analysis of immunogenicity

The ATP cohort for analysis of immunogenicity will include all evaluable subjects (i.e. those meeting all eligibility criteria, complying with the procedures defined in the protocol, with no elimination criteria during the study) for whom data concerning immunogenicity endpoint measures are available.

#### 10.6.4. According to protocol (ATP) cohort for analysis of efficacy

The ATP cohort for analysis of efficacy will include all evaluable subjects (i.e. those meeting all eligibility criteria, complying with the procedures defined in the protocol, with no elimination criteria during the study) for whom data concerning efficacy endpoint measures are available.

# 10.7. Derived and transformed data

- Seroprotection rate for HBsAg is defined as the percentage of subjects with antibody titers greater than or equal to an established cut-off (anti-HBsAg  $\ge$  10 mIU/mL).
- Seroprotection rate for Diphtheria is defined as the percentage of subjects with antibody titers greater than or equal to an established cut-off (anti-diphtheria  $\geq 0.1$  IU/mL).
- Seroprotection rate for Tetanus is defined as the percentage of subjects with antibody titers greater than or equal to an established cut-off (anti-tetanus  $\geq 0.1$  IU/mL).
- Seroprotection rate for PRP is defined as the percentage of subjects with antibody titers greater than or equal to an established cut-off (anti-PRP  $\ge 0.15 \ \mu g/mL$ ).
- A subject seropositive for anti-BPT antibody is a subject whose antibody titer is greater than or equal to the cut-off value (anti-BPT  $\geq$  15 EL.U/mL).
- A subject seropositive for anti-CS antibody is a subject whose antibody titer is greater than or equal to the cut-off value (anti-CS  $\ge 0.5$  EU/mL).
- Vaccine response is defined as follows:
  - The appearance of antibodies one month post Dose 3 (titer ≥ cut-off) in initially seronegative subjects (seroconversion)
  - Post vaccination antibody titers ≥ pre-vaccination titers in initially sero-positive subjects
- The Geometric Mean Titers (GMTs) calculations are performed by taking the anti-log of the mean of the log10 titer transformations. Antibody titers below the cut-off of the assay will be given an arbitrary value of half the cut-off for the purpose of GMT calculation.
- The Geometric Mean Concentration (GMC) calculations are performed by taking the anti-log of the mean of the log10 concentration transformations. Antibody concentrations below the cut-off of the assay will be given an arbitrary value of half the cut-off for the purpose of GMC calculation.

For a given subject and a given immunogenicity measurement, missing or non-evaluable measurements will not be replaced. Therefore, an analysis will exclude subjects with missing or non-evaluable measurements.

For the analysis of solicited local/general symptoms, only subjects for which information on the solicited local/general symptom sheet is available for the considered study dose will be included in the analysis.

